2.3 Study Endpoints

2.3.1 Safety

The primary study endpoints are the binary measures of occurrence or not of valve thrombosis, thromboembolism (TE), all major and minor bleeding events, whether or not related to drug therapy, reoperation, explant and death. The sum of all TEs (including valve thrombosis events) and major bleeding is used as the primary decision criterion for the primary endpoints.

Secondary safety study endpoints are other valve related adverse events (AEs) including the occurrence or not of endocarditis, hemolysis, hemolytic anemia, paravalvular leak and structural and non-structural dysfunction. All events shall be as defined by the AATS/STS guidelines [Akins CW, Miller DC, Turino MI, et al] for reporting valve study results.

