4. SAMPLE SIZE CONSIDERATIONS

The study is expected to test the safety of low dose (LD) therapy for anticoagulant therapy in On-X valve patients with LD therapy consisting of the use of Coumadin® in combination with aspirin or the use of antiplatelet therapy alone. The sample size for this study was designed as a non-inferiority study requiring only that LD therapy is not inferior to standard Coumadin®/aspirin treatment. It was necessary for the sample size calculation to assume an acceptable event rate for the primary endpoints of thromboembolism, thrombosis and bleeding events derived by summing the FDA OPC's. The incident rate of the sum of these three events needs to be at least as low as the OPC sum, 7.3%.

The test group will need to have less than 6%/ptyr cumulative rate of the three events for the study to reach significance with a patient population of 200 per group followed for 5 years at a statistical power of 80% with type I error of 0.05 and a maximum allowable difference between groups of 1.5%.

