6.5 Significance Level

Unless otherwise noted, all statistical analyses will be conducted with a significance level (α) of 0.05 and utilize two-sided testing.

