9. SAFETY ANALYSIS

9.1 Primary Analysis

The primary study endpoints are the binary measure of occurrence or not of valve thrombosis, thromboembolism, all major and minor bleeding events whether or not related to valve, reoperation, explant and death. Additionally, the sum of all TEs (including valve thrombosis events) and major bleeding will be included with the primary endpoint analyses.

For each of these binary endpoints, a Kaplan-Meier (KM) life table will be fitted and used to compare each valve treatment group and its control group. The KM analysis will adjust for select risk factors

including age and gender. In addition, the linearized rates as well as overall percentages of occurrences will be included in summary tables. Comparisons of overall percentages between each valve treatment group and its control will be made using a chi-square test or Fisher's exact test as appropriate. Linearized rates will be analyzed for differences between treatment and control groups with relative risks and 95% confidence intervals.

Analyses of mitral valve subjects will also be stratified by location (North America versus Italy) in the summary tables.

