9.2 Secondary Analysis

Secondary safety study endpoints are the occurrence or not of other valve related adverse events including endocarditis, hemolysis, hemolytic anemia, paravalvular leak and structural and non-structural dysfunction. All events shall be as defined by the AATS/STS guidelines [Akins CW, Miller DC, Turino MI, et al] for reporting valve study results.

For each of these binary endpoints, a Kaplan-Meier life table will be fitted and used to compare each valve treatment group and its control group. The KM analysis will adjust for risk factors age and gender. In addition, the linearized rates as well as overall percentages of occurrences will be included in summary tables. Comparisons of overall frequencies and percentages between each valve treatment group and its control will be made using a chi-square test or Fisher's exact test as appropriate. Linearized rates will be analyzed for differences between treatment and control groups with relative risks and 95% confidence intervals.

Analyses of mitral valve subjects will also be stratified by location (North America and Italy) in the summary tables.

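### SAP 9.1 and 9.2 turn neither the 1.5%/pt-yr non-inferiority margin nor the R < 2R_A OPC test into an analysis or decision rule

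*SAP*

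**What the plan says.** Protocol II.D bases the number of patients on two criteria. First, linearized rates of the primary events in each test group must be non-inferior to its control. The margin is 1.5% beside rates in %/ptyr, with 80% power and type I error 0.05, one-sided in Table 1. Second, for each event with an OPC, the null hypothesis R ≥ 2R_A must be rejected.

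SAP 4 describes a trial "designed as a non-inferiority study requiring only that LD therapy is not inferior", with "a maximum allowable difference between groups of 1.5" percent. SAP 3.1 keeps the comparison with the OPCs as part of the design. SAP 2.3.1 names what the decision rests on: "The sum of all TEs (including valve thrombosis events) and major bleeding is used as the primary decision criterion for the primary endpoints".

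The analysis sections then plan the following:

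- **SAP 9.1 (primary):** Kaplan-Meier comparisons, chi-square or Fisher tests of percentages, and for rates: "Linearized rates will be analyzed for differences between treatment and control groups with relative risks and 95% confidence intervals".
- **SAP 9.2 (secondary):** the same methods, including "Comparisons of overall frequencies and percentages between each valve treatment group and its control".
- **SAP 6.5:** "Unless otherwise noted, all statistical analyses will be conducted with a significance level (α) of 0.05 and utilize two-sided testing".
- **Protocol III.H:** life tables and linearized rates, with no test named.
- **SAP 14.1 (displays):** linearized-rate tables, including 14.3.32.1 to .3 after randomization, but no margin or OPC display.

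**The concern.** The trial was sized for a non-inferiority test that its SAP does not specify. The methods in SAP 9.1 and 9.2 look for differences. The SAP does not say how a relative risk with a 95% interval leads to a non-inferiority conclusion: the margin is absolute, no ratio margin is given, and the error level is one-sided 0.05 in Table 1 but two-sided 0.05 in SAP 6.5. The primary decision criterion of SAP 2.3.1 comes without a rule.

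The composite is also unsettled. SAP 4 sizes on "thromboembolism, thrombosis and bleeding events derived by summing the FDA OPC's", while SAP 2.3.1 counts major bleeding only. A fixed 1.5-point margin is looser in relative terms if the control rate of the narrower composite is lower.

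At stake is the pass/fail rule for reducing anticoagulation in patients with mechanical valves. Scale, error level, composite and OPC rule could all be settled after the data are known.

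**Working it through.** **Inputs.** Control rate 7.3%, test rate 6.0%, margin 1.5%, power 80%, one-sided 0.05 (Protocol II.D, Table 1). About 1000 patient-years per group (Protocol II.D). Equal allocation (SAP 3.1). OPC rates 0.8, 3.0, 3.5, 1.5, 1.2 and 1.2 per 100 valve-years (Protocol II.D); the sizing sum is 0.8 + 3.0 + 3.5 = 7.3.

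**1. The plan's own figure.** Table 1 gives 992. The Farrington-Manning formula for non-inferiority of two proportions uses restricted null rates of 6.04% (control) and 7.54% (test), so V0 = 0.1265; under the alternative, V1 = 0.073×0.927 + 0.060×0.940 = 0.1241. Then n = [(1.645√0.1265 + 0.842√0.1241)/(0.015 + 0.013)]² ≈ 991.2, rounded up to 992. The same method matches all 24 rows of Table 1, so the sizing is a non-inferiority calculation.

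**2. Power at 1000 patient-years per arm, 6.0% versus 7.3%.**

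- Two-sided difference test on the log relative risk: SE = √(1/60 + 1/73) = 0.1743; z = ln(73/60)/0.1743 = 1.125; Φ(1.125 − 1.960) = 20%.
- Relative risk against a converted margin: (7.3 + 1.5)/7.3 = 1.205; z = (0.1869 + 0.1961)/0.1743 = 2.198. Power is Φ(2.198 − 1.645) = 71% at one-sided 0.05, or Φ(2.198 − 1.960) = 59% with the two-sided 95% interval.
- Margin test on the rate difference, Poisson: SE = √(0.133/1000) = 0.01153; Φ(0.028/0.01153 − 1.645) = 78%. With binomial SE 0.01114 it is 81%. At one-sided 0.025 the two figures are 68% and 71%.
- Patient-years for 80% power with Poisson variance: (1.645 + 0.842)² × 0.133/0.028² ≈ 1049.

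**3. True rate on the margin, 8.8% versus 7.3%.** SE = √(1/88 + 1/73) = 0.1583; z = 0.1869/0.1583 = 1.180. P(no significant difference) = 1 − Φ(1.180 − 1.960) − Φ(−1.180 − 1.960) = 78%.

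**4. Two possible results (1000 patient-years per arm).**

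| Events, test vs control | Relative risk (95% CI) | One-sided 95% upper limit of difference | 1.5 margin |
|---|---|---|---|
| 60 vs 73 | 0.82 (0.58 to 1.16) | −1.3 + 1.645√133/10 = +0.60 | met |
| 73 vs 73 | 1.00 (0.72 to 1.38) | 0 + 1.645√146/10 = +1.99 | not met |

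Neither result is a significant difference, yet the protocol's criterion separates them.

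**5. OPC test.** With 1000 patient-years, find the largest count k whose exact one-sided 95% Poisson upper limit, χ²(0.95; 2k+2)/2, is below 2R_A × 1000. Power is P(X ≤ k) at R = R_A.

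| R_A (%) | Largest k | Power |
|---|---|---|
| 0.8 | 9 | 72% |
| 1.2 | 15 | 84% |
| 1.5 | 20 | 92% |
| 3.0 | 47 | over 99% |
| 3.5 | 56 | over 99% |

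**6. What 1.5 points means as a ratio.** 8.8/7.3 = 1.205; at assumed control rates of 5%, 4% and 3% it is 1.30, 1.375 and 1.50.

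**The case against.** The strongest reply is that the criteria are in the plan. Protocol II.D states both, SAP 4 repeats the margin and error rate, SAP 3.1 keeps the OPC comparison, and tables 14.3.32.1 to .3 will hold the rates that both need. SAP 9.1 also never says that the relative-risk interval is to be read against 1. With 60 versus 73 events its upper limit, 1.16, lies below 1.205, so the planned interval would meet a converted margin.

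Much of this stands. A reader might infer that the SAP's methods cannot answer the non-inferiority question, that the loss is the full gap between 20% and about 80% power, or that the OPC comparison will not be run at all. The documents support none of these. A relative-risk interval can test non-inferiority once a ratio margin is set, at 59% to 71% power under the design rates, and the OPC comparison remains a stated part of the design.

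A reader might also take this SAP 4 sentence as a third pass/fail threshold: "The incident rate of the sum of these three events needs to be at least as low as the OPC sum, 7.3" percent. It directly follows the statement that the sample size calculation had to assume an acceptable rate, so it reads as a sizing assumption.

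What the reply does not supply is the rule itself. Nothing ties the margin to an estimate, a scale, an interval level or the SAP 2.3.1 composite, and no OPC test method is given.

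**Conclusion.** The point holds and should be fixed before analysis. The protocol's two criteria are stated as design intent but not made operational: SAP 9.1 and 9.2 contain no margin comparison and no R < 2R_A test. This is more than missing detail, because absence of a significant difference does not track the protocol's criterion. A design-rate result of 60 versus 73 events meets the margin and 73 versus 73 does not, though neither differs significantly, and about 78% of trials truly on the margin would show no significant difference.

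The figures assume 1000 patient-years per arm, equal allocation, independent events, and rates of 7.3% and 6.0%. The last two belong to the sizing composite. The documents state no control rate for thromboembolism plus major bleeding, so power for that composite cannot be taken from these numbers. The margin is read as 1.5%/pt-yr because it stands beside rates in that unit. OPC power uses the protocol's R_A values and assumes R = R_A.

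**What to change.** **Margin test.** In SAP 9.1, for each test/control pair, make the primary analysis of the SAP 2.3.1 composite the one-sided 95% upper limit of the low-dose minus control difference in post-randomization linearized rate. Declare non-inferiority only if it is below 1.5%/pt-yr. For the low-risk AVR arm, which Protocol II.C reports as closed, follow its close-out plan. Exempt this test from SAP 6.5, reconcile it with the binary endpoint wording in SAP 2.3.1 and 9.1, and label the Kaplan-Meier, chi-square/Fisher and relative-risk analyses supportive. State the power: about 78% at 1000 patient-years with Poisson variance, or 68% to 71% at one-sided 0.025.

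**Composite.** Use one composite in SAP 4 and SAP 2.3.1, give its expected control rate, and confirm that 1.5 points still applies to it.

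**OPC test.** First state which source governs: the protocol cites the 1994 FDA draft guidance, the SAP cites ISO 5840:2005 and the 2010 FDA draft. Then, for each OPC event and test group, compare a one-sided 95% Poisson upper limit with 2R_A and report the power, including 72% at R_A 0.8 under the protocol's values.

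**Cost.** SAP wording, a margin line in tables 14.3.32.1 to .3, and one OPC table per test group. No new data items are needed. If 80% power is wanted with Poisson variance, about 1049 patient-years per group are needed rather than 1000; at one-sided 0.025, Table 1 lists 1260.

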9.2 Secondary Analysis

Secondary safety study endpoints are the occurrence or not of other valve related adverse events including endocarditis, hemolysis, hemolytic anemia, paravalvular leak and structural and non-structural dysfunction. All events shall be as defined by the AATS/STS guidelines [Akins CW, Miller DC, Turino MI, et al] for reporting valve study results.

For each of these binary endpoints, a Kaplan-Meier life table will be fitted and used to compare each valve treatment group and its control group. The KM analysis will adjust for risk factors age and gender. In addition, the linearized rates as well as overall percentages of occurrences will be included in summary tables. Comparisons of overall frequencies and percentages between each valve treatment group and its control will be made using a chi-square test or Fisher's exact test as appropriate. Linearized rates will be analyzed for differences between treatment and control groups with relative risks and 95% confidence intervals.

Analyses of mitral valve subjects will also be stratified by location (North America and Italy) in the summary tables.

9.3 Complications and Death

All Complications will be included in comprehensive data listings sorted by treatment group and subject. Any AEs resulting in death will be included in a separate data listing.

9.4 Hemolysis Laboratory Evaluations

Descriptive summaries of results will be presented by laboratory test and treatment group.

A data listing will display all laboratory test results and findings.

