On going hemolysis shall be defined by plasma free hemoglobin elevated to 125% of laboratory upper normal and serum lactate dehydrogenase (SLDH) values at greater than twice (200%) the laboratory upper normal unless the cellular source of the SLDH can be determined to be other than the red blood cell as evidenced by isoenzyme elevation of LD3, LD4 or LD5, and/or clinical evidence of recent myocardial infarction. Plasma free hemoglobin, serum haptoglobin, reticulocyte count and SLDH shall be tested whenever hemolysis is suspected in any patient and SLDH isoenzymes shall be fractionated whenever the SLDH test value is above 175% of upper normal.

Unanticipated Valve-Related Event

It is unknown what kind of event would qualify for the use of this form, but it is supplied in case any unknown valve-related complication should arise that does not meet any other defined criterion. Should this happen this event must be reported to the monitor immediately, since it is likely to create immediate regulatory reporting requirements. An occurrence of an unknown negative effect is very serious and must not be left unreported for any length of time.

Congestive Heart Failure

Congestive heart failure will be considered valve related if the event is new and is not continued from a preoperative heart failure condition, and is caused by one of the

following prosthesis-related events: Anticoagulant-related hemorrhage, endocarditis, hemolysis, nonstructural dysfunction, paravalvular leak, structural deterioration, thromboembolism, thrombosis, or reoperation.

The most common causes of non-valve related congestive heart failure are coronary artery disease, hypertension, valvular heart disease (due to a valve other than the study valve), cardiomyopathy, cor pulmonale, congenital heart disease, or unknown causes. When an event is considered not valve related the reasons for that decision must be recorded.

Other Cardiovascular and Pulmonary Complications

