	CVA] Fatal	
2 \Box Valve Thrombosis			
3. 🔲 Bleeding Event	\square Major \square Minor		
Cerebral Cardiac	Ocular GI Nose	bleed 🗌 Hematoma 🗌 Other	
4. Prosthetic Endocarditis (Organis	m:))	
Risk Factor: Dental Work	IV Drug Use \Box H	Recent Infection Other	
5. Prosthetic Valve Dysfunction			
□ Nonstructural	(Туре:)	
Structural	(Туре:)	
Paravalvular Leak	(I Minor I Major)		
6. Hemolysis (conduct blood tests)			
7. Hemolytic Anemia (conduct blood tests) Primary Secondary to:			
8. Congestive Heart Failure	Ualve Related	□ Not Valve Related	
9. \Box Reoperation	□ Repair □ Exp	blant	
10. Other Valve Related	Explain:		
11. \Box Death - Primary Cause: \Box V	alve related D Other cardiac	Other Unknown	
(continues next page	.)	

Institution	MCRI On-X®	Dationt Initials	
Institution.	Low Dose Anticoagulation Study	ratient initials	
Investigator:	CRF 4	Patient No.	
	Complications 2 of 2		
Complication number:			
Treatment: None Medication	Hospitalization	Surgery (Complete CRF5	j)
Patient Condition at Time of Event			
Cardiac Rhythm	\square_{Paced} \square_{Atria}	l Fibrillation	
Other			
NYHA Class		Unknown	
Anticoagulant Therapy 🛛 Warfarin	Clopidogrel H	eparin	
INR: Aspirin	□ _{None} □ _O	ther	
Outcome:			
Event Fully Resolved			
Permanent Impairment (Spec	vify)
)
Death Date (d/m/y):	//		
Autopsy L Y	es L _{No}		
Explant Y	es 🗌 No (If yes, com	plete CRF-5)	
Relationship to Device:			
Valve Related: Yes	🗌 No		
Lab Test Results for Hemolysis, as needed	1:		
Plasma Free Hemoglobin	Lab Upper Normal		
SLDH Lab Upper Normal	(LD1, LD2, 1	LD3, LD4	, LD5)
Reticulocyte Count Lab U	Upper Normal	_	
Serum Haptoglobin Lab L	ower Normal	-	
Investigator Signature:	Date	e (m/d/y):/	_/

Institution: Investigator:	MCRI On-X [®] Low Dose Anticoagulation Study CRF 5 Reoperative Data	Patient Initials	
	Reoperative Data		
Reoperative Procedure: Procedure Dat	te (m/d/y)://		
Study Valve Replacement (complete Explant data below)	Aortic Replacement Value Mitral Size:	ve Mfg: _mm Type:	
$\Box \text{ Study Valve Repair } \Box \text{ Aort}$	ic Specify:al		
CABG			
Pacer Implantation			
Aneurysm Repair			
	Position:		
Non Study Valve	nt Procedure:		
Repair	Replacement Valve M	fg:	
	Size:mm	Туре:	
Explant Condition: Reop C (check all that apply)	Autopsy Explant Date (1	n/d/y)://	
Pannus Overgrowth			
Thrombus			
□ Vegetation Organism:			
Other Specify:			
Valves Returned: Yes Date F	Returned (m/d/y):/	_/	
└── No If No,	Explain,		
Investigator Signature:	Date	e (m/d/y):/	/

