6.6 Statistical Notation and Methodology

Unless stated otherwise, the term "descriptive statistics" refers to the number of subjects (n), mean, median, standard deviation (SD), minimum, and maximum for continuous data and frequencies and percentages for categorical data. Unless otherwise noted, all data collected during the study will be included in data listings and will be sorted by treatment group, subject number and then by date/time within each subject number.

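### The hemolysis laboratory tables in SAP 9.4 make no use of the laboratory limits on which the protocol's hemolysis definition rests, so they cannot show how many patients meet it

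*SAP*

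**What the plan says.** - **Definition (Protocol III.C, Hemolysis).** "On going hemolysis shall be defined by plasma free hemoglobin elevated to 125% of laboratory upper normal", together with SLDH "values at greater than twice (200%) the laboratory upper normal". An exception applies where the SLDH is shown to come from a source other than red cells. Both criteria are relative to the laboratory's own limit; neither is an absolute value. Isoenzymes are to be fractionated once SLDH passes 175% of upper normal.
- **When tests are done.** The four tests (plasma free hemoglobin, haptoglobin, reticulocyte count, SLDH) "shall be tested whenever hemolysis is suspected in any patient". They are not scheduled visit assessments. CRF 4 carries the same condition: "Lab Test Results for Hemolysis, as needed".
- **What is collected (CRF 4, page 2).** Each result has a field for the laboratory's limit next to it, for example "SLDH Lab Upper Normal". The limit is the upper normal for plasma free hemoglobin, SLDH and reticulocytes, and the lower normal for haptoglobin.
- **What is planned (SAP 9.4).** "Descriptive summaries of results will be presented by laboratory test and treatment group", plus a listing of all results. SAP 6.6 gives the content: n, mean, median, "standard deviation (SD), minimum, and maximum for continuous data and frequencies and percentages for categorical data". The displays are tables 14.3.50.1 to 14.3.51.3 (before and after randomization, three valve groups) and listing 16.2.20.
- **Derivations (SAP 7.3).** Echocardiographic quantities and body surface area only.
- **The endpoint (SAP 9.2).** Hemolysis and hemolytic anemia are binary secondary safety endpoints. They are compared with control by Kaplan-Meier, chi-square or Fisher's exact test, and linearized rates with relative risks and 95% confidence intervals. Events are defined there by the AATS/STS reporting guidelines.

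**The concern.** The protocol's criterion works on one scale and the planned table on another. A mean, median or maximum SLDH in laboratory units cannot be read against a rule stated as a multiple of a limit that differs between laboratories. The text available names no central laboratory for these tests, and a limit field beside every result suggests that limits are expected to vary. The protocol allows up to 50 centers in three countries (the SAP says 40, United States only). As far as the text shows, CRF 4 prints no units for these tests, whereas CRF 6 does for echocardiography.

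At stake is whether the laboratory data can support the hemolysis endpoint. SAP 9.2 does not cite the 125%/200% rule, and SAP 9.4 leaves out the limits needed to apply it. So no planned display checks the reported events against the protocol's numeric definition, although every field needed for that is collected.

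**Working it through.** The plan gives no figure here to reproduce. The check sets the texts side by side and adds two illustrations with assumed limits, because the documents give no reference values.

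**1. Texts compared**

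| Element | Protocol III.C and CRF 4 | SAP 6.6, 7.3, 9.4 |
|---|---|---|
| Scale | multiple of the laboratory's limit | not stated; no ratio derived |
| Threshold | 125% (free hemoglobin) and above 200% (SLDH) | none |
| Limit | recorded beside each result | not used in any summary |
| Patients covered | those in whom hemolysis is suspected | number randomized and number meeting the definition not given |

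The SAP does not use the word raw. That results would be summarised as reported is inferred from what 6.6, 7.3 and 9.4 leave out.

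**2. Can an unscaled value be classified?** Percent of normal = 100 × result / upper normal. Take SLDH = 450 U/L and assumed upper normals of 180 to 300 U/L:

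- 450/180 = 250%
- 450/200 = 225%
- 450/225 = 200%
- 450/250 = 180%
- 450/300 = 150%

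The SLDH criterion (above 200%) is met at the first two laboratories and not at the other three. At the last, the value is also below the 175% isoenzyme trigger. A table in U/L shows one number for all five.

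**3. Can the laboratory mix alone create an arm difference?** Suppose both arms have the same mean multiple of normal, r. Two laboratories have upper normals U and kU, and the share of tests done at the second differs by d between arms, centred on 50%. The spurious difference is D = r × U × (k − 1) × d. With assumed r = 1.5 and U = 200 U/L, D and its percentage of the lower arm's mean are:

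| k | d = 5 points | d = 10 points | d = 20 points |
|---|---|---|---|
| 1.1 | 1.5 U/L (0.5%) | 3.0 (1.0%) | 6.0 (1.9%) |
| 1.25 | 3.8 (1.1%) | 7.5 (2.2%) | 15.0 (4.5%) |
| 1.5 | 7.5 (2.0%) | 15.0 (4.1%) | 30.0 (8.3%) |
| 2.0 | 15.0 (3.4%) | 30.0 (6.9%) | 60.0 (14.3%) |

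Example: k = 1.5 and d = 0.10 give 1.5 × 200 × 0.5 × 0.10 = 15 U/L. The lower arm's mean is 300 × (0.55 + 1.5 × 0.45) = 367.5, and 15/367.5 = 4.1%.

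Few tested patients make larger imbalances easier. With four tested per arm (assumed), three against two at the second laboratory and k = 1.5, the means are 300 × (0.25 + 1.5 × 0.75) = 412.5 and 300 × (0.5 + 1.5 × 0.5) = 375. The difference is 37.5 U/L, or 10%.

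A reversed sign needs an extreme case. If one arm is tested wholly where the limit is 200 and averages 1.6 times normal, its mean is 320 U/L. If the other is tested wholly where the limit is 300 and averages 1.2 times normal, its mean is 360 U/L.

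On the ratio scale the difference in every cell of the table, and in the four-patient example, is exactly 0, because both arms have r = 1.5.

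**4. What the ratio does not mend.** Testing follows suspicion, which arises after randomization. On either scale the table describes tested patients, not the arm. Stating the numbers tested and randomized makes this visible but does not remove it.

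**The case against.** The strongest reply is that hemolysis is already counted. Protocol III.C, under complication reporting, says that its own definitions govern how complications are reported. The 125%/200% rule is one of them, and item 6 on CRF 4 is a hemolysis box with an instruction to do blood tests. The site can therefore apply the rule with its own laboratory's limits, and SAP 9.2 compares the resulting event between arms. This stands. A reader might infer that patients who cross the threshold go uncounted or that the harm cannot be seen; the documents do not support that. What remains is narrower: SAP 9.2 refers to the AATS/STS guidelines and not to the III.C rule, so the SAP does not say that the binary event will be checked against the limits. Whether those guidelines contain the same rule cannot be judged from the documents.

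A second reply is that SAP 9.4 plans no test between arms, unlike SAP 8.5, 8.6 and 10, and that randomization balances laboratories in expectation. This too largely stands. A reader might infer that the table will mislead on arm differences or get their sign wrong. That rests on assumed limits, laboratory mix and patient numbers. Balance among tested patients is nevertheless not assured, since testing is selective and the protocol says only that the randomization module can stratify, not that it does so by center.

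Third, every result is listed, so single cases can be inspected. That is true, but a listing gives no count per arm.

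Last, the stakes are low: both arms carry the same valve, and the primary decision criterion in SAP 2.3.1 is thromboembolism plus major bleeding. This limits the point to a minor one.

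**Conclusion.** The point holds as a minor defect in a supporting safety table. The tables planned in SAP 9.4 combine results whose meaning depends on the testing laboratory, set aside a limit that is already recorded, and cannot show how many patients meet the protocol's definition of hemolysis. The between-arm comparison of the hemolysis event in SAP 9.2 is unaffected, and the trial's main conclusion does not depend on these tables.

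The conclusion rests on two inferences: that SAP 9.4 means results as reported, and that more than one laboratory with differing limits supplies them. The size of any distortion is not known. Over the table of assumed scenarios it runs from 0.5% to 14.3% of the lower arm's mean. It is small unless limits differ widely and the arms' laboratory mix is clearly unbalanced.

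**What to change.** In the SAP:

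1. **7.3:** derive plasma free hemoglobin, SLDH and reticulocyte count as multiples of the upper normal recorded on CRF 4, and haptoglobin as a multiple of its recorded lower normal.
2. **9.4 and tables 14.3.50 and 14.3.51:** summarise these multiples. Report per arm the number randomized, the number tested and the number meeting the existing III.C definition, including its exception for SLDH from other sources. Add a note that testing is on suspicion, so the table describes tested patients only.
3. **9.2:** state how that count relates to the reported hemolysis event, and list the patients in whom the two disagree.

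The cost is a few sentences and a few lines of programming. All result and limit fields are already on CRF 4, no new data are needed, and no clinical rule changes.
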